3. STUDY CONDUCT

3.1 RANDOMIZATION ISSUES

Eligible patients will be randomized in a 1:1 ratio to either receiving atezolizumab (arm A) or observation (arm B) with the use of a stratified permuted–block randomization.

The randomization will be stratified for the following factors:

- PD–L1 status (IC0/1 vs. IC2/3)
- Nodal status (positive vs. negative)
- Tumor stage after surgical resection (≤pT2 vs. pT3/pT4)
- Prior neo–adjuvant chemotherapy (yes vs. no)
- Number of lymph nodes resected (< 10 vs. ≥ 10)

3.2 DATA MONITORING

An independent Data Monitoring Committee (iDMC) will be convened to evaluate safety data until the analysis of the primary endpoint (DFS), after which iDMC review of the study data will be discontinued. The iDMC will evaluate study safety data on a periodic

basis, approximately every 6 months after enrollment of the first patient. Members of the iDMC will be external to the Sponsor and will follow a charter that outlines their roles and responsibilities. The Sponsor will remain blinded to the results until the analysis of the primary endpoint of DFS. All summaries and analyses by treatment arm for the iDMC review will be prepared by an external independent data coordinating center.

4. STATISTICAL METHODS

4.1 ANALYSIS POPULATIONS

4.1.1 Intent-To-Treat Population

The ITT population is defined as all randomized patients, whether or not the patient received the assigned treatment (atezolizumab/observation).

4.1.2 Safety Population

The safety population is defined as patients who received at least one dose of atezolizumab, and all patients who did not receive any dose of atezolizumab who had at least one post-baseline safety assessment (e.g., adverse event, lab, vital signs, ECG, etc.), regardless of their assigned treatment (atezolizumab/observation).

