5.3.1 Adverse Event Reporting Period

Investigators will seek information on adverse events at each patient contact. All adverse events, whether reported by the patient or noted by study personnel, will be recorded in the patient’s medical record and on the Adverse Event eCRF.

After informed consent has been obtained **but prior to initiation of study drug** for patients in Arm A or prior to the Cycle 1, Day 1 visit for patients in Arm B, only serious adverse events caused by a protocol-mandated intervention (e.g., invasive procedures such as biopsies, discontinuation of medications) should be reported (see Section 5.4.2 for instructions for reporting serious adverse events).

For patients in Arm A, after initiation of study drug, all serious adverse events and adverse events of special interest, regardless of relationship to study drug, will be reported until 90 days after the last dose of study drug or until the initiation of another anti-cancer therapy, whichever occurs first. All other adverse events, regardless of relationship to study drug, will be reported until 30 days after the last dose of study drug or until the initiation of another anti-cancer therapy, whichever occurs first.

For patients in Arm B, all adverse events occurring from the date of the Cycle 1, Day 1 visit until 30 days after the last day of the observation period or until the start of an anti-cancer therapy (whichever occurs first) will be reported.

Instructions for reporting adverse events that occur after the adverse event reporting period are provided in Section 5.6.

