6.5 SAFETY ANALYSES

Safety analyses will include all patients who received at least one dose of study treatment (atezolizumab) and all patients randomized to the observation arm with at least one safety assessment. Exposure to atezolizumab treatment and length of safety follow-up will be summarized by arm.

Verbatim descriptions of adverse events will be mapped to MedDRA terms. Treatment-emergent events (defined as events occurring on or after the first dose of atezolizumab, or, for patients in the observation arm, after the date of randomization) will be summarized by MedDRA term, appropriate MedDRA levels, and NCI CTCAE v4.0 grade. For each patient, the maximum severity reported will be used in the summaries. Adverse events will be summarized regardless of relationship to study drug as assessed by the investigator. All adverse events, adverse events leading to withdrawal of study drug, adverse events leading to dose reduction or interruption, Grade ≥ 3 adverse events, serious adverse events, and adverse events of special interest will be summarized. Deaths and cause of death will be summarized.

Changes in NCI CTCAE grade for selected laboratory tests will be tabulated by arm. Changes in selected vital signs will be summarized. ATA results will be summarized and listed by patient for patients in Arm A only.

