1. BACKGROUND

This Statistical Analysis Plan (SAP) provides details of the planned analyses and statistical methods for Study WO29636 (IMvigor010). The analyses described in this SAP will supersede those specified in Protocol WO29636.

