4.4.4 Sensitivity Analyses

4.4.4.1 Sensitivity Analyses on DFS for Patients in Any Treatment Arm Receiving Protocol Prohibited Anti-Cancer Therapy

The impact of protocol prohibited anti-cancer therapy on DFS may be assessed depending on the number of patients who receive such therapy before a DFS event. If $> 5\%$ of patients received protocol prohibited anti-cancer therapy before a DFS event in any treatment arm, data for these patients will be censored at the last disease assessment date before they received such therapy in DFS analyses that may be performed for the comparisons between treatment arms.

4.4.4.2 Sensitivity Analyses on OS for Patients in Observation Arm Receiving Atezolizumab or Similar Immunotherapy

The impact on OS by patients in observation arm subsequently receiving atezolizumab or another immunotherapy considered similar to atezolizumab in its mechanism of action may be assessed, depending on the number of such patients. If more than 5% of

patients in observation arm have received atezolizumab or a similar immunotherapy, the following analyses may be performed to compare treatment arms at each of the interim analyses and final analysis, as applicable:

- OS in the observation arm will be discounted according to a range of possible effects on OS after having received atezolizumab or another immunotherapy (e.g., 10%, 20%, 30%, etc.)
- Additional sensitivity analyses may be conducted if deemed necessary

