4.5 SAFETY ANALYSES

Unless specified otherwise, the safety analyses described below will be conducted for the safety population (see Section 4.1.2), with patients grouped according to whether any atezolizumab treatment was received (i.e., patients who received any dose of atezolizumab will be included in the atezolizumab arm).

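### SAP 4.1.2 and 4.5 put never-dosed Arm A patients in the observation column for safety, although their adverse events are collected less fully and Protocol 6.5 keeps them out

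*SAP*

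**What the plan says.** SAP 4.1.2 builds the safety population from two parts. One is patients with at least one dose of atezolizumab. The other is "all patients who did not receive any dose of atezolizumab who had at least one post-baseline safety assessment", and the definition applies "regardless of their assigned treatment (atezolizumab/observation"). SAP 4.5 then forms the groups by receipt: "patients who received any dose of atezolizumab will be included in the atezolizumab arm". Undosed patients who qualify fall in the other column.

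Protocol 6.5 draws the line differently. Its treated part is "all patients who received at least one dose of study treatment (atezolizumab"). Its comparator is "all patients randomized to the observation arm with at least one safety assessment". A never-dosed Arm A patient is in neither part. SAP Section 1 settles which document governs: "The analyses described in this SAP will supersede those specified in Protocol WO29636".

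On event collection, Protocol 5.3.1 says that Arm A patients before first dose report "only serious adverse events caused by a protocol-mandated intervention", and Protocol 5.4.2.1 repeats the restriction. For Arm B the restriction ends at the Cycle 1 Day 1 visit, after which all adverse events are reported until the end of that arm's reporting period.

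**The concern.** The SAP column used as the comparator pools two kinds of patient. Those randomised to observation have all adverse events recorded for up to a year plus 30 days. Those randomised to atezolizumab but never dosed have, under Protocol 5.3.1, only a narrow class of serious events recorded. Both count fully in the denominator, so the column's rates are pulled down by how data are collected and not by patients' health.

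What is at stake is the comparison of adverse event rates in an open-label trial against no active treatment, where the observation column supplies the background rate. An understated background rate makes atezolizumab look relatively worse. The effect is likely to be small. Still, it comes from an explicit grouping rule that departs from the protocol, and the SAP gives no reason for the change.

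**Working it through.** **Step 1: trace one patient.** Take a patient randomised to Arm A who never receives a dose and has a safety assessment after baseline.

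- Protocol 6.5: not treated and not randomised to observation, so in neither group.
- SAP 4.1.2: undosed with an assessment, and assigned arm is ignored, so in the safety population.
- SAP 4.5: no atezolizumab received, so in the non-atezolizumab column.

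**Step 2: which events can that patient contribute?**

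- Protocol 5.3.1 and 5.4.2.1: only SAEs attributed to a study-required procedure, because first dose never occurs.
- Protocol Appendix 1, footnote x (repeated in SAP Appendix 2): the SAE-only restriction ends at randomisation. This conflicts with 5.3.1. The Arm A window in the same footnote is counted from the last dose, which this patient does not have.
- SAP 4.5.2: treatment-emergent events start at first dose or, for the observation arm, after randomisation. The SAP does not say which start applies to an Arm A patient shown in the observation column.
- SAP 4.3: baseline in the atezolizumab arm is anchored to first administration, so post-baseline has no anchor for this patient.

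Event capture is therefore truncated under 5.3.1, and unsettled once footnote x is read beside it.

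**Step 3: size.** The plan gives no figure to reproduce, so this is an illustration.

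- From the documents: 800 patients randomised 1:1, so N = 400 per arm.
- Assumed: k = 8 to 20 never-dosed Arm A patients qualify (2% to 5% of 400), all 400 observation patients are in the column, and the true observation rate is p = 40%.
- Assumed: the k patients contribute no events.

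Displayed rate = p × N / (N + k).

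| k | Calculation | Displayed rate | Shift |
|---|---|---|---|
| 8 | 0.40 × 400/408 | 39.2% | 0.8 points |
| 20 | 0.40 × 400/420 | 38.1% | 1.9 points |

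The multipliers are 400/408 = 0.980 and 400/420 = 0.952. Zero events is the extreme case, so these are the largest downward shifts for those counts. Any event these patients do contribute makes the shift smaller.

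**The case against.** Grouping safety data by treatment received is ordinary practice, and Protocol 6.5 also defines its treated group by receipt. The SAP says openly that it supersedes the protocol. Few patients are likely to be affected: Appendix 1 footnote r asks for the first dose on the day of randomisation, or at most 7 days later. Because post-baseline is undefined for a never-dosed patient, it is also unclear how many would qualify. The safety analyses are descriptive summaries, and the bias runs against the sponsor's drug. All of this stands and limits the size of the point. It does not explain why patients under a narrower reporting rule should share a denominator with the observation arm.

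Two stronger readings are tempting, and the documents do not support either.

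- **That the added patients have no collected events.** They enter only with a safety assessment, which SAP 4.1.2 allows to be an adverse event. Procedure-related SAEs are collected in any case, and footnote x points to fuller reporting from randomisation.
- **That observation patients who later receive commercial atezolizumab move to the treated column and dilute its rates.** The unqualified wording of SAP 4.5 permits this literally, and SAP 4.4.4.2 foresees "patients in observation arm subsequently receiving atezolizumab or another immunotherapy". But SAP 4.5.1 summarises exposure for Arm A only, SAP 4.7 lists antibody results for Arm A only, SAP Section 2 bars crossover within the study, and Protocol 6.5 refers to study treatment. Study drug is the more natural meaning, and on that meaning the effect is zero. The 5% trigger in SAP 4.4.4.2 gives no estimate of it either: it concerns OS, also counts similar immunotherapies, and is a threshold, not a forecast. This is an ambiguity to close, and no effect size should be attached to it.

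**Conclusion.** The point holds for never-dosed Arm A patients. SAP 4.1.2 and 4.5 place those with a qualifying assessment in the observation column, contrary to Protocol 6.5. Under Protocol 5.3.1 and 5.4.2.1 their events are captured less fully than those of the patients they join, so observation rates are biased slightly downward.

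For 8 to 20 such patients and a true rate of 40%, the shift is at most 0.8 to 1.9 percentage points. The counts, the rate and the absence of events are all assumptions. The true effect may be close to zero if almost everyone in Arm A is dosed, or if reporting in practice follows footnote x. The change is worth making because it is simple and removes a departure from the protocol, not because the bias is large.

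**What to change.** In SAP 4.1.2 and 4.5, restore the Protocol 6.5 groups:

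- **Treated:** patients who received at least one dose of atezolizumab as study treatment.
- **Comparator:** patients randomised to observation who have at least one safety assessment and received no atezolizumab as study treatment. The last condition is an addition to Protocol 6.5, so that nobody belongs to both groups.
- **Never-dosed Arm A patients:** shown in a separate listing with whatever events were recorded.

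Specifying study treatment also settles where observation patients who later receive non-study atezolizumab belong.

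Separately, reconcile Protocol 5.3.1 and 5.4.2.1 with Appendix 1 footnote x, and with its copy in SAP Appendix 2, on when the SAE-only restriction ends for Arm A.

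The cost is SAP wording, one listing and a clarification of the reporting period. The regrouping needs no new data, and it should be settled before the safety tables are produced.

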4.1.3 Pharmacokinetic-Evaluable Population

The pharmacokinetic-evaluable population is defined as all patients who received any dose of atezolizumab and who have evaluable pharmacokinetic (PK) samples.

4.1.4 ADA-Evaluable Population

The anti-drug antibodies (ADA)-evaluable population is defined as all patients treated with atezolizumab who have at least one post-baseline ADA result.

4.1.5 Patient-Reported Outcome-Evaluable Population

The patient-reported outcome (PRO) evaluable population is defined as all randomized patients with baseline and at least one post-baseline PRO assessment.

4.2 ANALYSIS OF STUDY CONDUCT

Enrollment, major protocol deviations (including major deviations of inclusion/exclusion criteria), and reasons for discontinuation from the study will be summarized overall and by treatment arm for the ITT population. Study treatment administration and reasons for discontinuation from study treatment will be summarized for patients in the safety population. Length of follow up will be summarized by treatment arm for the ITT population.

4.3 ANALYSIS OF TREATMENT GROUP COMPARABILITY

Demographic variables (age, sex, race/ethnicity), stratification factors (nodal status, number of lymph nodes resected, tumor stage, PD-L1 status, and prior neo-adjuvant chemotherapy) and baseline and disease characteristics (e.g., ACCL, time since initial

diagnosis, time since surgery, surgery-related information, type of urinary diversion, and Eastern Cooperative Oncology Group [ECOG] Performance Status) will be summarized by treatment arm for the ITT population.

Unless otherwise noted, the baseline value of any variable will be defined as the last available value prior to the first administration of study treatment for the atezolizumab arm and prior to Cycle 1 Day 1 date of observation for the observation arm. Descriptive statistics (mean, median, SD, range) will be presented for continuous variables, and frequencies and percentages will be presented for categorical variables.

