2.4 PATIENT-REPORTED OUTCOME OBJECTIVE

The PRO objective for this study is as follows:

- To assess health status as measured by the EuroQol 5-dimension, 5-level version (EQ-5D-5L) questionnaire

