4.5.13.2 Assessments during Treatment/Observation

All visits must occur within ± 3 days from the scheduled date unless otherwise noted (see [Appendix 1](#)). All assessments will be performed on the day of the specified visit unless a time window is specified. Assessments scheduled on the day of study treatment administration (Day 1) of each cycle should be performed prior to study

treatment infusion unless otherwise noted. Local laboratory assessments from each cycle must be reviewed prior to study treatment administration for each cycle.

See the table provided in [Appendix 1](#) for the schedule of treatment/observation period assessments.

The following assessments may be performed ≤ 96 hours before Day 1 of each cycle: ECOG performance status, limited physical examination, local/central laboratory tests, adverse event evaluation, and concomitant medication evaluation.

For patients in Arm A, if scheduled dosing is precluded because of a holiday, then dosing may be postponed to the soonest following date, with subsequent dosing continuing on a 21-day schedule. If treatment was postponed for fewer than 2 days, the patient can resume the original schedule. For patients in both arms, if scheduled study assessments cannot be obtained because of a holiday, these assessments should then be obtained at the soonest following date, provided that the soonest following date is not within 2 days of other regularly scheduled study assessments.

Assessments for disease recurrence should continue to occur as specified in Section [4.5.5](#), regardless of treatment delays.

After five cycles have been completed, one cycle may be delayed by 1 week (i.e., 28 days instead of 21 days for one cycle) for one time to allow for vacations.

Blood samples for pharmacodynamic biomarker analysis and pharmacokinetics will be obtained for patients in Arm A according to the schedule in [Appendix 2](#).

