6.3 SUMMARIES OF TREATMENT GROUP COMPARABILITY

Demographic variables such as age, sex, race/ethnicity, stratification factors (nodal status, number of lymph nodes resected, tumor stage, PD-L1 status, and prior neoadjuvant chemotherapy), baseline and disease characteristics (e.g., ACCI, time since initial diagnosis, time since surgery, surgery-related information, type of urinary diversion, and ECOG Performance Status) will be summarized by treatment arm for all randomized patients. Continuous variables will be summarized using means, standard deviations, medians, and ranges. Categorical variables will be summarized by proportions.

The baseline value of any variable will be defined as the last available value prior to the first administration of study treatment.

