6.7 PATIENT-REPORTED OUTCOME ANALYSES

Results from the EQ-5D-5L (VAS) will be summarized descriptively for each timepoint as mean and median values, as well as mean and median change from baseline.

The first five questions of the EQ-5D-5L will be used to build utilities for health economic modeling and will be summarized in a separate report.

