Appendix 1 Schedule of Assessments (cont.)

Study Procedures	Both Arms	Arm A (Atezolizumab)		Arm B (Observation)			Both Arms
	Screening for Randomization	All Cycles	Discontinuation ^a	Cycles 1, 3, 5, 7, 9, 11, 13, and 15	Cycles 2, 4, 6, 8, 10, 12, 14, and 16	Discontinuation ^a	Follow-Up
	Days –28 to –1	Day 1 (± 3 Days for Cycles ≥ 2) ^b	≤ 30 Days after Last Dose	Day 1 (± 3 Days for Cycles ≥ 2) ^b	Day 1 (± 3 Days) ^b	≤ 30 Days after Last Visit	
Adverse events ^x	x	x	x	x	x	x	
Telephone contact ^y					x		
Survival and anticancer therapy follow-up ^z							x
Patient-reported outcomes ^{aa}		x ^{bb}	x	x		x	x

Note: For Arm A, assessments scheduled on the days of study treatment infusions should be performed before the infusion unless otherwise noted.

- ^a Patients will be asked to return to the clinic for a discontinuation visit not more than 30 days after the decision to discontinue treatment/observation early, or after the end of the one-year treatment/observation period.
- ^b After five cycles have been completed, one cycle may be delayed by 1 week (i.e., 28 days instead of 21 days for one cycle) for one time to allow for vacations.
- ^c Written informed consent is required for performing any study-specific tests or procedures. Written informed consent (on the main study Informed Consent Form) can be obtained outside the 28 days screening period prior to randomization. Prior to signing the main consent form for the study, patients may specifically allow for the collection and testing of archival or fresh tumor tissue by signing the pre-screening consent form. Results of standard-of-care tests or examinations performed prior to obtaining informed consent and within 28 days prior to randomization (except where otherwise specified) may be used for screening assessments rather than repeating such tests.
- ^d Cancer history includes stage, date of diagnosis, and prior anti-tumor treatment. Demographic information includes sex, age, and self-reported race/ethnicity.
- ^e Serum pregnancy test (for women of childbearing potential, including women who have had a tubal ligation) must be performed and documented as negative within 14 days prior to Cycle 1 Day 1. Starting from Cycle 3, either serum or urine pregnancy test (positive urine test results will be confirmed with a serum pregnancy test) must be performed every two cycles during the study treatment, and as clinically indicated thereafter.

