- ^{aa} The PRO questionnaire EQ-5D-5L will be completed by the patients at the investigational site. All PRO questionnaires are required to be administered prior to administration of study treatment (Arm A) and/or prior to any other study assessment(s) to ensure that the validity of the instrument is not compromised and to ensure that data quality meets regulatory requirements. Study personnel should review all questionnaires for completeness before the patient leaves the investigational site, and the hard copy originals of the questionnaires must be maintained as part of the patient's medical record when relevant at the site for source data verification. After discontinuation of the treatment/observation period, for patients who have not experienced disease recurrence, the EQ-5D-5L will be administered at the same schedule as the assessments for disease recurrence (see Section 4.5.5). The EQ-5D-5L will also be recorded at 6, 12, and 24 weeks after disease recurrence per telephone interview by trained site staff and in compliance with best practices and recommendations by EuroQol. Study personnel will record patient responses on a paper copy of the EQ-5D-5L during the telephone interview as record of source documentation. *After the primary analysis, the EQ-5D-5L assessments are no longer required for patients who are in disease recurrence follow-up or who have had a DFS event.*
- ^{bb} Odd-numbered cycles only (i.e., Cycles 1, 3, 5, 7, 9, 11, 13, and 15).

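### SAP 4.3 requires the observation-arm baseline to pre-date Cycle 1 Day 1, but the first EQ-5D-5L falls on that day, so Arm B has no scheduled baseline for its planned change scores

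*SAP*

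**What the plan says.** SAP Section 4.3 gives a baseline rule for every variable unless another section says otherwise. In Arm A, baseline is the last value before the first administration of atezolizumab. In Arm B, it is the last value "prior to Cycle 1 Day 1 date of observation for the observation arm".

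Both schedules of assessments (Protocol Appendix 1 and SAP Appendix 2) have a row headed "Patient-reported outcomes". Its screening cell is empty. For Arm A, a footnote limits the questionnaire to "Odd-numbered cycles only (i.e., Cycles 1, 3, 5, 7, 9, 11, 13, and 15". For Arm B, the row is marked in the odd-cycle column, which also begins at Cycle 1. Protocol Section 4.5.10 agrees: it describes six-weekly administration during treatment or observation and then during follow-up, and mentions no screening questionnaire.

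Several planned outputs need a baseline:

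- Protocol Section 6.7 plans VAS means and medians by timepoint, "as well as mean and median change from baseline".
- SAP Section 4.8 plans change scores for utilities, items and VAS, and a longitudinal mixed model for VAS change with between-arm differences.
- Under SAP Section 4.1.5, the PRO "evaluable population is defined as all randomized patients with baseline and at least one post-baseline PRO assessment".

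**The concern.** The two arms have different kinds of anchor. Arm A is anchored to an event, the first infusion, so a value obtained earlier the same day counts. Arm B is anchored to a calendar date, so a value obtained on that date is not prior to it. For variables also measured at screening, such as ECOG status or laboratory tests, this hardly matters, because an earlier value exists. For the EQ-5D-5L, nothing earlier is scheduled.

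At stake is the only planned between-arm comparison of change in patient-reported health status. If the rule is applied literally, the only Arm B patients with a baseline are any who happened to complete a questionnaire early and off schedule, and they need not represent the arm. If the rule is set aside, the departure is made at programming rather than in the plan. The trial is open-label and the outcome is subjective, so the choice is better written down beforehand.

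**Working it through.** The plan states no figure on this point to reproduce. The check is whether any scheduled questionnaire meets the rule in each arm.

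**Inputs**

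- Cycle length is 21 days and EQ-5D-5L cycles are 1, 3, 5, 7, 9, 11, 13 and 15 in both arms (Protocol Appendix 1, SAP Appendix 2).
- Screening questionnaires: 0 (same schedules).
- About 800 patients, randomized 1:1 (SAP Sections 2 and 2.2), so 800 / 2 = 400 per arm.
- Baseline rule: SAP 4.3.

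**Scheduled days.** With Cycle 1 Day 1 as Day 1, the questionnaire in cycle c falls on Day 1 + 21 × (c − 1). This gives Days 1, 43, 85, 127, 169, 211, 253 and 295, which is 8 questionnaires. Those at discontinuation and in follow-up come later and cannot be baselines.

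**Applying SAP 4.3**

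| | Condition | Qualifying questionnaires | On-period change scores per patient |
|---|---|---|---|
| Arm A, as written | before first dose | 1 (Day 1, pre-dose) | 8 − 1 = 7 |
| Arm B, as written | day < 1 | 0 | 0 |
| Arm B, Cycle 1 Day 1 named as baseline | day ≤ 1 | 1 | 8 − 1 = 7 |

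The Arm A entry relies on the Appendix 1 footnote requiring the questionnaire before study drug is given.

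**Does any window move the Arm B questionnaire earlier?**

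- Protocol 4.5.13.2 puts assessments on the visit day unless a window is given.
- The ±3-day window on the odd-cycle column applies only from Cycle 2.
- The 96-hour early allowance in Protocol 4.5.13.2 covers "ECOG performance status, limited physical examination, local/central laboratory tests, adverse event evaluation, and concomitant medication evaluation". The EQ-5D-5L is not listed.
- The footnote requiring PRO completion before other assessments fixes the order within a visit, not an earlier date.

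**Does any other text supply a baseline?**

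- SAP 4.1.5 and 4.8 use the term baseline without defining it for the EQ-5D-5L, and SAP 4.9 addresses only the efficacy endpoints.
- Protocol 6.3 has baseline "defined as the last available value prior to the first administration of study treatment", an event that does not occur under Arm B's assigned management. SAP Section 1 also states that the SAP's analyses supersede the protocol's.

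No scheduled Arm B questionnaire qualifies: 0 of about 400 patients have a scheduled baseline, against about 400 in Arm A.

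**The case against.** The strongest reply is that the intent is plain. The questionnaire must be completed before any other assessment at the visit, and SAP 4.1.5 and 4.8 both presuppose a baseline in each arm. The Cycle 1 questionnaire is the only scheduled candidate. A reading that empties Arm B defeats the SAP's own PRO sections, so a programmer would use the Cycle 1 value and little room would remain for a data-driven choice. The data are collected either way, and the between-group PRO comparison is descriptive. On this view the point is one of wording.

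Much of that stands. The likely intent is as described, and the consequence is limited. The protocol's PRO objective is only "To assess health status as measured by the EuroQol 5-dimension, 5-level version (EQ-5D-5L) questionnaire". It is also fair that the count of patients describes the schedule and does not measure bias or lost precision. In addition, the rule speaks of the last available value, so an off-schedule questionnaire completed before Cycle 1 Day 1 would qualify.

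It does not remove the problem. SAP 4.3 added a separate Arm B anchor and worded it as a date, so this is a stated rule that excludes the value evidently intended. The proviso allowing exceptions would accommodate one, but no exception is recorded. It is also fair to be cautious about an empty cell in a machine-read table. Here the two schedules agree, and the text of Protocol 4.5.10 supports them independently.

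**Conclusion.** The concern holds. As written, SAP 4.3 leaves the observation arm without a scheduled EQ-5D-5L baseline. Three SAP 4.8 outputs cannot be produced for patients assessed on schedule: the Arm B change-from-baseline summaries (also planned in Protocol 6.7), the mixed-model between-arm difference in VAS change, and the Arm B part of the optional PRO-evaluable sensitivity analysis.

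By-arm summaries of raw scores, completion rates, DFS, OS and type I error control are untouched, as are variables with a screening value. An empty Arm B baseline would be noticed in programming, so the exposure is an undocumented decision and not a hidden bias. This should be corrected, but it does not threaten the trial's main conclusions.

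The conclusion assumes that prior to a date excludes that date, that questionnaires are completed on the scheduled day, and that Arm A's first dose is given on Cycle 1 Day 1 after the questionnaire.

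**What to change.** Add one sentence to SAP Section 4.8: *The Cycle 1 Day 1 EQ-5D-5L (pre-dose in Arm A) is the baseline in both arms.* The opening proviso of SAP 4.3 permits a variable-specific definition, so the general rule and the baselines of all other variables can stay as they are.

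Each arm then has one scheduled baseline and seven on-period post-baseline questionnaires, the first at Cycle 3 (Day 43 − Day 1 = 42 days, or 6 weeks). The change summaries, the VAS model and the PRO-evaluable population can then be produced as planned. The cost is one sentence, with no new data and no effect on any other analysis.
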